7.6.3 Analyses of Exploratory Efficacy Endpoints

Exploratory endpoints will be summarized using the mITT population, with data collected after discontinuation of treatment excluded but without consideration of any protocol deviations. Details of all analyses to be performed on the exploratory endpoints will be detailed in the SAP.

Analyses of biomarkers will be addressed in a data analysis plan outside the study SAP.

A further exploratory analysis will be performed on the Week 16 results. Adjusted indirect comparisons, pivoted around placebo, will be performed against publicly available data from two studies in apremilast in mild/moderate or moderate psoriasis. Further details will be provided in the study SAP.

7.6.4 Pharmacokinetic Analyses

The number and percentage of participants who have a quantifiable concentration of EDP1815 in their blood sample will be summarized using the safety set by visit. Placebo participants will be pooled into a single treatment group. If at least 20% of participants within a treatment group are found to have a quantifiable level at one of the visits, then the concentration will be summarized as a continuous variable for the relevant treatment group at that visit.

7.6.5 Safety Analyses

All safety endpoints will be tabulated or plotted by treatment group using the safety set. All safety analyses will use the pooled placebo group. Further details will be described in the SAP.

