3.1.1 Rationale for Study Design

The EDP1815 Phase 1 program evaluated doses of 1.6×10^{10} cells to 8.0×10^{11} cells given daily for 2 weeks in healthy volunteers and doses of 1.6×10^{11} cells and 8.0×10^{11} cells given daily for 4 weeks to participants with mild to moderate psoriasis. All doses were found to be well tolerated and doses of both 1.6×10^{11} and 8.0×10^{11} cells induced clinically relevant reductions in signs and symptoms of plaque psoriasis and psoriasis lesion severity.

The doses tested in the program are based on predictions from the preclinical data and the clinical and biomarker data obtained in EDP1815-101, the Phase 1 study. All doses tested up to 8.0×10^{11} cells have been equally well tolerated. No clear difference in efficacy was observed between the 1.6×10^{11} cells and the 8.0×10^{11} cells in EDP1815-101 over the 28-day dosing period, but at the 14-day follow up (Day 42) the participants receiving the higher dose had a continued improvement in their psoriasis compared to participants who had received the lower dose. This suggests a more sustained and potentially deeper response in the high dose group. Evelo is therefore proposing to include the lowest and highest feasible doses (based on capsule load) in this study to establish the dose response, the maximum clinical benefit, and to assess participant tolerability and acceptability of the doses tested.

The clinical response to EDP1815 treatment will be evaluated using multiple assessments, facilitating appropriate selection of efficacy measures for future studies.

The use of a placebo comparator is appropriate for this participant population of individuals with mild to moderate plaque psoriasis for the following reasons:

- The limited proven efficacy of other treatments (topical corticosteroids, vitamin D3 analogs, and apremilast) in patients with mild to moderate plaque psoriasis that could potentially serve as an active comparator
- The limited duration of the study (maximum of 16 weeks of treatment) for each participant
- A randomization ratio of 2:1 for EDP1815 treatment to placebo treatment in each cohort

Part B of the study, which includes additional visits at Weeks 24, 28, and 40, is designed to help understand the durability of treatment effect, including time to relapse and incidence of

Evelo Biosciences Inc.

EDP1815

Protocol: EDP1815-201 Version 5.0 (Amendment 4)

17 November 2020

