5.1 Method of Assigning Participants to Treatment Groups

Participants will be randomly assigned at the baseline visit (Visit 2) to 1 of 3 cohorts (in a 1:1:1 allocation ratio) that are distinguishable to participants and study staff by the number of capsules administered per once-daily dose. Within the cohort, participants will be randomly assigned in a 2:1 allocation ratio to receive either EDP1815 or matching placebo treatment (Section 3.1). Interactive response technology will be used to administer the randomization schedule.

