5.9 Dose Modification

Dose adjustments, including dose interruptions, and/or decreasing the dose frequency may be allowed for safety or tolerability (including capsule load) after consultation with the sponsor medical monitor.

6 Study Assessments and Procedures

Before performing any study procedures, all potential participants will sign an ICF.

Additional procedural details related to the ICF are provided in Section 9.3.

The SoA is presented in Table 6-1. Detailed instructions for study site activities will be provided in the appropriate specific user manual, where applicable. High level descriptions of the study assessments are presented in the subsections of Section 6. In exceptional circumstances, study assessments may be conducted remotely (ie, at a participant's home), except for screening, baseline, Visit 9, and Visit 10. Remote visits can only occur if operationally possible.

Table 6-1 Schedule of Assessments – Part A

Procedure	Screening	Baseline	Treatment Period								Follow-up ^{a, b}
Day	-28 to -7	1	8	15	22	29	43	57	85	113	141
Week	-4	0	1	2	3	4	6	8	12	16	20
Visit number	1	2	3	4	5	6	7	8	9	10	11
Visit window (days)	--	--	5-11	12-18	19-25	26-32	40-46	54-60	82-88	110-116	141-148
Informed consent	X										
Inclusion and exclusion criteria	X	X ^c									
Demography	X										
HbsAg, HCV and HIV screening	X										
HLA sample ^d		X									
Medical history and current medical conditions (including duration of psoriasis)	X	X									
Full physical examination (height only at screening) ^e	X	X	X			X			X	X	X
Pregnancy test ^f	X	X								X	X
Laboratory assessments (hematology, serum biochemistry and CRP, and urinalysis)	X	X				X		X	X	X	X
Fasting ^g blood sampling		X						X		X	
12-lead ECG ^h	X	X				X				X	X
Vital signs ⁱ	X	X	X	X	X	X	X	X	X	X	X
Randomization		X									
Dosing ^j		X	X	X	X	X	X	X	X		
Dispense study drug		X	X	X	X	X	X	X	X		
Collect/count unused study drug			X	X	X	X	X	X	X	X	
Skin plaque biopsies ^k		X								X	

Procedure	Screening	Baseline	Treatment Period								Follow-up ^{a, b}
Day	-28 to -7	1	8	15	22	29	43	57	85	113	141
Week	-4	0	1	2	3	4	6	8	12	16	20
Visit number	1	2	3	4	5	6	7	8	9	10	11
Visit window (days)	--	--	5-11	12-18	19-25	26-32	40-46	54-60	82-88	110-116	141-148
Digital photography of lesion sites ¹		X				X		X		X	X
Stool samples for microbiome investigation ^m		X								X	X
Dispense stool diary	X										
Collect/record stool diary		X									
Blood sample for detection of systemic EDP1815		X								X	

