- Placebo 10 capsules
- EDP1815 10 capsules
- All Placebo
- All EDP1815
- Total

For concomitant medication, efficacy and safety outputs, columns will be ordered and labelled as follows:

- All Placebo
- EDP1815 1 capsule
- EDP1815 4 capsules
- EDP1815 10 capsules
- All EDP1815 (concomitant medication and safety only)

For the efficacy analyses, if the 3 cohorts of placebo participants are found to be too heterogeneous for pooling, selected efficacy tables will also be presented by treatment within cohort, in which case columns will be ordered and labelled as:

- Placebo 1 capsule
- EDP1815 1 capsule
- Placebo 4 capsules
- EDP1815 4 capsules
- Placebo 10 capsules
- EDP1815 10 capsules

For the primary analysis:

- For study disposition summaries where it is appropriate to report information on participants who failed screening, the enrolled population will be used.
- For safety summaries, the safety population will be used.
- For all other summaries and analyses the mITT population will be used, with selected efficacy outputs reproduced using the per-protocol population.

For the final analysis:

- For partial relapse and complete relapse endpoints analysis Week 16 Responders population will be used.
- For duration endpoints and rebound analysis mITT population will be used.
- For or all other summaries and analyses the Part B population will be used.

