9.1 Pooling of Placebo Cohorts

The assumption that the 3 cohorts of placebo participants can be pooled into a single placebo group to be used as a control for all active doses will be examined using mean (\pm SD) and box plots of percent change in PASI score against time. In addition, a mixed model for repeated measures (MMRM) model will be used to compare the 3 cohorts of placebo participants. The model will include parameters for cohort, visit and baseline PASI score together with cohort*visit and baseline PASI score*visit interactions. LS mean (95% CI) estimates for each placebo cohort will be plotted by visit.

A decision will be made by the Evelo study team, based on examination of the above figures and model, on whether the pooling strategy is appropriate.

If any placebo cohort is considered too different from the other placebo cohorts then no pooling will be used. The pooling of 2 cohorts only will not be considered.

If the pooling strategy is considered appropriate, then the placebo cohorts will be pooled into a single 'all placebo' group for all efficacy analyses and will be used as a common control group for each active EDP1815 treatment group.

If the assumption of similarity across the placebo groups is found to be unreasonable, each placebo dose will be included in the model as a separate dose level and pairwise comparisons between each active EDP1815 dose and placebo will be performed using only the matching placebo dose data from the same cohort.

All efficacy data will be listed, including both individual item scores and calculated questionnaire summary scores.

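### Dose-specific safety columns have only a placebo control pooled over 1, 4 and 10 capsules, so an apparent adverse-event dose trend could mix capsule load with EDP1815

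*Protocol*

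**What the plan says.** Protocol 7.6.5 is unconditional: "All safety analyses will use the pooled placebo group". SAP Section 8 carries this through. "For concomitant medication, efficacy and safety outputs, columns will be ordered and labelled as follows": All Placebo, then EDP1815 1, 4 and 10 capsules, then All EDP1815 (the last for concomitant medication and safety only). None of the safety tables listed in SAP 15.3.1 or 15.5.1 is given a cohort-specific placebo column.

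Efficacy is treated differently. SAP 9.1 examines whether the placebo cohorts can be pooled, using mean plots, "box plots of percent change in PASI score against time" and a placebo-only MMRM. The alternative layout in SAP Section 8 is likewise limited: "For the efficacy analyses, if the 3 cohorts of placebo participants are found to be too heterogeneous for pooling, selected efficacy tables" may be shown by treatment within cohort. No safety variable enters the check, and safety has no fallback.

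The same section of the SAP already prints all six arms (placebo and EDP1815 at 1, 4 and 10 capsules) for disposition, baseline data and compliance.

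Protocol 5.1 says the cohorts are "distinguishable to participants and study staff by the number of capsules administered per once-daily dose". Protocol 3.1.1 gives one aim as "to assess participant tolerability and acceptability of the doses tested", and Protocol 2.2 bases the choice of optimal dose on efficacy and safety together.

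**The concern.** Randomisation within each cohort supplies a control that takes the same number of capsules and is blinded to content. The planned adverse-event tables do not show it. In the 10-capsule comparison, two thirds of the pooled control took 1 or 4 capsules and knew it. In the 1-capsule comparison, two thirds of the control took more capsules than the active group.

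If swallowing more capsules, or knowing that one does, changes adverse events or their reporting, the 1-capsule dose will look better than its matched contrast and the 10-capsule dose worse. A reader looking for a dose-tolerability pattern could not tell from these tables whether the same gradient is present under placebo. That matters because safety by dose feeds the optimal-dose objective.

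**Working it through.** **Inputs from the documents.** There are about 75 participants per cohort, three cohorts at 1:1:1, and 2:1 within cohort (Protocol 3.1). That gives 50 active and 25 placebo per cohort, and 3 × 25 = 75 pooled placebo, as in Protocol 7.3. The only power figures are for efficacy (difference 20, SD 25, two-sided 5%). With 42 active completers against 63 pooled placebo I get 98.0% (stated: more than 95%). Against 21 matched placebo I get 84.9% (stated: more than 80%). Both are reproduced, but neither speaks to safety.

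**Assumed inputs.** The documents give no adverse-event rates by capsule count. The rates below are assumptions. In each scenario the rate depends on capsule count only and EDP1815 has no effect.

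**Expected contrasts.** Pooled placebo rate = (p1 + p4 + p10)/3. Apparent difference for a dose = its rate minus the pooled rate. Within-cohort difference = 0 by construction.

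For 5/8/15%: pooled = 28/3 = 9.3%. The differences are 5 − 9.3 = −4.3, 8 − 9.3 = −1.3 and 15 − 9.3 = +5.7 points. The risk ratio at 10 capsules is 15/9.33 = 1.61.

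| Assumed rates at 1/4/10 capsules | Pooled placebo | Apparent differences (points) |
|---|---|---|
| 10/12/16% | 12.7% | −2.7, −0.7, +3.3 |
| 5/8/15% | 9.3% | −4.3, −1.3, +5.7 |
| 10/15/25% | 16.7% | −6.7, −1.7, +8.3 |
| 5/10/25% | 13.3% | −8.3, −3.3, +11.7 |
| 10/10/10% | 10.0% | 0, 0, 0 |

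**All EDP1815 versus All Placebo.** Both columns have the same 1:1:1 capsule mix. In the 5/8/15% case each is expected at 9.3%, so the difference is 0. This contrast is not confounded.

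**How often a trend would look convincing.** No safety test is planned, so this is only a gauge. In 200,000 simulated trials, a nominal 5% Cochran-Armitage trend over 0/1/4/10 capsules with pooled placebo was positive in 13% (10/12/16%) and 38% (10/15/25%). A slope fitted to the within-cohort differences was positive in 4.8% and 5.1%.

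**Precision.** Root-mean-square error = √(bias² + variance). The variance with pooled placebo is p(1−p)/50 for the active arm plus 25·Σp(1−p)/75² for placebo. With matched placebo it is p(1−p)(1/50 + 1/25) and the bias is 0.

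For 10 capsules at 5/8/15%:
- Pooled: variance = 0.00255 + 25 × 0.2486/5625 = 0.00365; bias = 0.0567; error = √(0.00365 + 0.00321) = 8.3 points.
- Matched: √(0.1275 × 0.06) = 8.7 points.

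| Assumed rates | Error at 10 capsules, pooled | Error at 10 capsules, matched |
|---|---|---|
| 10/12/16% | 7.3 | 9.0 |
| 5/8/15% | 8.3 | 8.7 |
| 10/15/25% | 11.2 | 10.6 |
| 5/10/25% | 13.7 | 10.6 |

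The pooled contrast has the smaller error when the gradient is mild, and the matched contrast when it is steep.

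**The case against.** The case for leaving the tables alone is substantial, and most of it stands.

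- **An unconfounded contrast is already planned.** Whether EDP1815 adds adverse events beyond capsule load, averaged over doses, can be read from All EDP1815 against All Placebo. A reader might infer that every safety comparison is distorted. The documents do not support that; only the dose-specific columns are affected.
- **Some of the information is tabulated elsewhere.** Disposition uses the six-arm layout and includes reasons for stopping treatment (SAP 8.1). Listings are sorted by treatment and cohort, and Protocol 7.5 permits summaries by cohort. None of these, however, commits the SAP to adverse-event incidence beside the matched placebo.
- **The protocol does not predict a capsule-load problem.** Protocol 5.9 says only that adjustments "may be allowed for safety or tolerability (including capsule load"). That is a permission. Protocol 3.1.1 reports that the doses tested so far were equally well tolerated. A steep gradient has no support in the documents.
- **Pooling is a defensible choice for sparse counts.** With a mild gradient it has the smaller error, as shown above.
- **Poor tolerability of 10 capsules would be a real property of that dose as given.** This is true. The issue is what it is attributed to, and that bears on how a dose finding should be interpreted.
- **Matched placebo does not isolate the bacteria.** Protocol 5.3 lists mannitol and colloidal silicon dioxide in the active capsules only. Matching controls capsule number, not every ingredient.

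It would also be too strong to say that the matched control is discarded: the 10-capsule placebo participants remain as one third of the pooled column.

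**Conclusion.** The point holds in a limited form. The three dose-specific safety columns have a single control pooled over capsule counts, with no check of poolability and no fallback for safety. If capsule count affects adverse events or their reporting, an apparent dose trend mixes capsule load with EDP1815. Under the mildest and steepest gradients tabulated, the distortion at 10 capsules is +3.3 and +11.7 points with no drug effect; with no capsule effect it is 0. These figures rest entirely on assumed rates, so the true size is unknown, and the planned safety tables could not reveal it.

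A reader might go further and conclude that the plan will produce a false dose-toxicity signal. The documents do not establish that capsule count matters, the safety outputs are descriptive, and the overall active-placebo contrast is sound. The right label is a cheap improvement.

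**What to change.** In SAP Section 8, for at least Tables 14.3.1.1.1, 14.3.1.1.2, 14.3.1.2, 14.3.1.3 and 14.3.1.7, add the placebo 1-, 4- and 10-capsule columns already used for disposition. Keep All Placebo and All EDP1815. This takes these tables from five columns to eight. Amend Protocol 7.6.5 so that pooled placebo is used, with cohort-matched placebo also shown for the main adverse-event tables.

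State how the columns are to be read. The matched columns serve to check whether a gradient across doses also appears under placebo. The pooled column remains the reference for rare events.

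The cost is SAP wording and table programming, with no new data. Each matched placebo column has about 25 participants. At a 20% event rate the standard error of a risk difference rises from √(0.16 × (1/50 + 1/75)) = 7.3 points to √(0.16 × (1/50 + 1/25)) = 9.8 points, so single within-cohort differences should not be over-read. The layout is best fixed before any unblinded output, because four of the five tables are flagged for the interim and a split added after a trend appears would look data-driven.

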7.6.6 Other Analyses

Tabulations will be provided for completion/withdrawal status, protocol deviations, study populations, demographic and other baseline characteristics, use of concomitant medications, and exposure of and compliance with study drug.

7.6.7 Interim Analyses

An interim analysis may be undertaken during the conduct of the study after at least 50% of participants have completed at least 12 weeks of treatment or withdrawn from treatment. The purpose of this analyses will be to aid in the planning of future studies and for a better understanding of the benefit/risk profile of EDP1815.

For the interim analysis, unblinded aggregate results will be produced by an unblinded team within [REDACTED] and reviewed by Evelo personnel for strategic planning use. These will not be shared with any study site staff, participants, or clinical monitors who will be involved in the collection and review of individual study data.

The interim analysis will look at the primary endpoint of percentage change from baseline in PASI score, secondary, and safety endpoints. The posterior predictive probability (Spiegelhalter et al 2004) of the percent change from baseline in PASI score being at least 20% lower in each active dose compared to the pooled placebo will also be calculated, using the estimates of treatment difference found at Week 12 using the Bayesian MMRM described for the primary analysis. If the posterior predictive probabilities for all active doses are found to be <30%, then the study may be stopped for futility.

No decisions regarding study conduct, other than the potential to stop the study early for futility, will be made based on these assessments and the study will not be stopped if superior efficacy is found. Outputs featuring unblinded treatment assignments will be created by the unblinded analysis group within [REDACTED] and shared with selective Evelo personnel (to be included in the data dissemination plan).

Evelo Biosciences Inc.

EDP1815

Protocol: EDP1815-201 Version 5.0 (Amendment 4)

17 November 2020

Further details of the outputs that will be produced will be described in the SAP.

8 Data Quality Assurance

This study will be conducted according to the ICH E6(R2) risk and quality processes described in the applicable procedural documents. The quality management approach to be implemented in this study will be documented and will comply with the current ICH guidance on quality and risk management. The sponsor assumes accountability for actions delegated to other individuals (eg, Contract Research Organizations).

The sites will maintain source documentation and enter participant data into the eCRF as accurately as possible and will rapidly respond to any reported discrepancies. Electronic CRFs are accessed through Medidata Rave® (Medidata Solutions Inc, New York, New York). This EDC system is validated and compliant with US Title 21 CFR Part 11. Each person involved with the study will have an individual username and password that allows for record traceability. Thus, the system, and subsequently any investigative reviews, can identify coordinators, investigators, and individuals who have entered or modified records, as well as the time and date of any modifications. A quality review of the data will be performed by the site with additional reviews by the clinical monitor through source data verification.

Each eCRF is presented as an electronic copy, allowing data entry by site staff, who can add and edit data, identify and resolve discrepancies, and view records. This system provides immediate direct data transfer to the database, as well as immediate detection of discrepancies, enabling site coordinators to resolve and manage discrepancies in a timely manner.

Paper copies of the eCRFs and other database reports may be printed by the investigator. This system provides site staff, monitors, and reviewers with access to hard copy audits, discrepancy reviews, and investigator comment information.

After all data reviews and query resolutions are complete, the SAP is approved and signed, and any summary/analysis populations are approved, the database will be locked.

8.1 Data Management

As part of the responsibilities assumed by participating in the study, the investigator agrees to maintain adequate case histories for the participants treated as part of the research under this protocol. The investigator agrees to maintain accurate eCRFs and source documentation as part of the case histories. These source documents may include diaries, laboratory reports,

ECG strips, etc. Electronic devices will be used for the administration of investigator and participant responses to Clinical Outcome Assessments. Data collected via these devices will be uploaded directly to a central database for storage and analysis. Details will be provided in the specific user manual.

All eCRF information is to be completed. If an item is not available or is not applicable, this fact must be indicated. Blank spaces must not be present unless otherwise directed. Study site personnel will enter participant data into the Medidata Rave system. The analysis data sets will be a combination of these data and data from other sources (eg, laboratory data).

Clinical data management will be performed in accordance with applicable █ standards and data cleaning procedures to ensure the integrity of the data (eg, removing errors and inconsistencies in the data). Adverse events and medical history will be coded using the then-current MedDRA terminology. Concomitant medications will be coded using the most current available WHO Drug Dictionary.

After database lock, each study site will receive an electronic copy of their site-specific eCRF data as entered into the EDC system for the study, including full discrepancy and audit history. Additionally, an electronic copy of all the study site's data from the study will be created and sent to the sponsor for storage. █ will maintain a duplicate electronic copy for their records. In all cases, participant initials will not be collected or transmitted to the sponsor.

9 Ethics

